2.15.2 Sample Size Rationale

Based on the need for data collected from this study, it was determined that a total of 10 subjects will be required, including departures.

2.15.3 Patient Populations

Interim results may be collected and reported. All data will be analyzed at the end of the study. The primary analysis will be performed by the intention-to-treat approach. Everyone who begins the treatment is part of the study whether he or she completes the study or not. The most appropriate method of handling missing values will be chosen based on the individual trial goals, endpoints and context.

The analysis of demographic, medical history, and efficacy variables will be based on all patients who are randomized and receive at least one treatment. The analysis of safety data will be based on all patients who receive at least one treatment, and have at least some safety data.

2.15.4 Analysis of Demographic and Medical History Variables

Summaries will be prepared for all important demographic and medical history variables. For quantitative variables summaries will include the sample size, mean, median, standard deviation, minimum, and maximum. For these variables the treatment groups will be compared using either a t-test or a Wilcoxon Rank Sum test, as appropriate. For categorical variables the summaries will include the sample size and the number and percent of patients for each outcome. For these variables the treatment groups will be compared using Fisher's Exact test. Statistical significance will be declared if the two-sided p-value is < 0.05 .

2.15.5 Analysis of Efficacy Variables

Additional efficacy variable is the change from baseline to Visit 4 (90 day follow up visit).

Baseline is defined as the last assessment prior to the first treatment. The change from baseline to visits 3 and 4 will be analyzed using a Mixed Model Repeated Measures Analysis of Variance. A pairwise treatment group comparison at visit 4 will be performed using the results of this analysis. If a patient has no post-baseline assessment of the primary efficacy variable it will be assumed that the change from baseline to visit 4 is zero. The changes to visits 3 and 4 will be left as missing. Statistical significance with respect to the treatment group comparison at visit 4 will be declared if the two-sided p-value is < 0.05 . For each treatment group, summaries will be prepared for both the observed assessment and the change from baseline. The summaries will include the sample size,

mean, median, standard deviation, minimum, and maximum. The statistical significance of the mean change from baseline for each treatment group will be determined using a paired t-test.

2.15.6 Analysis of Safety Variables

Safety will be assessed through the degree of pain/discomfort related to the procedure (universal pain scale) and the collection of Adverse Events throughout the course of the study. For each treatment group these variables will be summarized. The summaries will include the number and percent of patients for each outcome. No statistical comparisons will be performed for any of these variables.

3.0 RISK ANALYSIS AND MANAGEMENT

3.1 Risk Determination

This device study used in this study does not meet the FDA definition for a Significant Risk Device study per 21 CFR 812.3(m). Therefore, the sponsor determines that this is a non-significant risk device study.

Significant risk device means an investigational device that:

- (1) Is intended as an implant and presents a potential for serious risk to the health, safety, or welfare of a subject;
- (2) Is purported or represented to be for a use in supporting or sustaining human life and presents a potential for serious risk to the health, safety, or welfare of a subject;
- (3) Is for a use of substantial importance in diagnosing, curing, mitigating, or treating disease, or otherwise preventing impairment of human health and presents a potential for serious risk to the health, safety, or welfare of a subject; or
- (4) Otherwise presents a potential for serious risk to the health, safety, or welfare of a subject.

3.2 Risk Management

The Investigator in this clinical trial has been invited to participate based on his/her previous experience with the use of the system and/or similar systems and industry experience. Experience with treatments is the most critical element in managing subject risk in this trial.

In addition, as with any study, there is a risk of bias. Objective evaluation methods may be used in conjunction with subjective evaluation methods when feasible. The value of the compensation to the clinical investigator for conducting the study is not influenced by the study outcome. If photographic results are listed as the primary objective, they are to be evaluated by blinded evaluators who did not partake in the study. If information concerning investigator assessment of improvement or investigator satisfaction is collected, then it is not listed as an objective for the study.

All other known risks will be disclosed to the subject via the informed consent process. Since this is an elective procedure and the subjects are volunteers, it can be assumed that their signature on the informed consent is indicative of their agreement to accept the risks involved.

The risks to the subjects who participate in this study are the same as those for the subject undergoing similar non-ablative radiofrequency treatment. It is possible to have an adverse reaction to the MyEllevate® procedure. There may be some side effects that we don't know about yet.

3.3 Risk Analysis

CONTEXT OF THE PROPOSED INVESTIGATION:

Aging of the neck is characterized by a loss of skin elasticity, and is often accompanied by increased submental fat, ptosis of the neck, and a weakening of the platysma muscle. As a result, the inferior border of the mandible often loses definition, prompting patients to seek surgical correction. Various surgical and nonsurgical techniques have been described to lift the neck, including laser skin resurfacing, submental liposuction, skin tightening procedures, skin excision procedures, platysmaplasty, suspension sutures, and modification of the digastric muscle. More invasive procedures carry increased risks of complications. Therefore, minimally-invasive procedures of the neck represent a safer approach to address the aging process of the neck and deliver the desired result of restoration.

ASSESSMENT OF RISKS OF THE PROPOSED INVESTIGATION:

The risk identified with the overall clinical investigation is the integrity of the data collected. There are multiple clinical mitigation strategies for the risks identified. Proper training on the device and protocol will be performed. Data from prior investigations will be utilized to minimize side effects and optimize treatment outcomes. Monitoring of the study will be implemented to minimize subject and data risks.

ASSESSMENT OF BENEFITS OF THE PROPOSED INVESTIGATION:

The subject may or may not have improvement for the indication treated.

CONSIDERATION OF PATIENT PREFERENCE INFORMATION:

Many physicians support the use of minimally invasive cosmetic treatments in response to high patient satisfaction of cosmetic results with the currently available procedures and device. However, there is still a level of interest in novel technologies that could reduce the risk of complications and the need for future treatments.

ASSESSMENT OF UNCERTAINTY:

There is uncertainty of the safety profile and efficacy results with the MyEllevate® procedure.

CONCLUSION:

This device is determined to be a non-significant risk study and will be using a device cleared for use by the FDA.

Patient population to be enrolled in this clinical study:

Total anticipated population: 10 Subjects

Age Range: 18 – 65 years of age

Gender: Male or Female

Condition: Visible platysma bands, glands and/or sagging in the submentum, jawline and/or neck.

[figure not shown]
[figure not shown]
[figure not shown]
4.0 DEVICE DESCRIPTION AND SPECIFICATIONS

Device Name	Date of 510(k)	Indication(s):
ICLED Surgical Suture System	09 October 2009 K091061	Indicated for soft tissue approximation and elevation of sub dermis and underlying muscle of the submentum & jawline

The ImplicitCare ICLED Surgical Suture System provides a minimally invasive means of performing reconstructive, plastic and cosmetic surgery procedures by eliminating the need for extensive subdermal undermining through a large incision. Rather, the suture is guided subcutaneously using rigid rods like blunt-tipped needles. The ICLED Surgical Suture System, is a sterile, single use device kit consisting of five (5) device components:

- 1.) Marking Tape: Intended to locate the marking sites of suture insertion. The backing of the tape is a medical acrylic adhesive
- 2.) Lancet: Intended to puncture the skin at the site of suture insertion. The Lancet creates a perforation just large enough to pass the Suturod™ and suture.
- 3.) Clearing Device: Intended to sweep away any dermal attachments for a 360° radius around the skin puncture made by the Lancet. This helps prevent “dermal tethering” as the suture is passed.
- 4.) Suturod™: Stainless steel, connected at the midpoint by a 100” (254 cm) length of USP 4-0 (1.5 Metric) TEVDEK® II braided nonabsorbable polyester Suture. The suture, acquired directly from Teleflex, is coated with polytetrafluoroethylene (PTFE) for improved handling characteristics and to reduce “tissue drag,” and is green in color.
- 5.) Light Tool (Handle): Contains an LED light source supplied by three (3) 1.55V silver oxide batteries, and which connects to the Suturod™. When connected, the light created by the LED passed through the fiber optic light pipe within the Suturod™ and Illuminates the distal tip. This permits visual verifications—through the dermis—of both the path and depth of the Suturod™ as it passed through the subdermal tissue.

Device Description	Device Image
Lancet: consists of a 400 series stainless steel blade in a polycarbonate handle.	

Device Description	Device Image
Clearing Device: right angled 300 series stainless steel rod 0.078" in diameter extending from the distal end of a polycarbonate handpiece.	
Suturod™ Rod: The Suturod™ is 0.078" in diameter, 8.5" long, is composed of 300 series stainless steel, and is hollow, with a fiber optic light pipe running the length of the Suturod™ internally.	
Light Handle: Consists of a polycarbonate handle into which the end of a Suturod™ may be connected. Simple mechanical switch internal to the Light Handle illuminates the LED as the Suturod™ is connected. The LED is a 5mm white LED rated at 25mA maximum at 3.6V. The LED is powered by three (3) silver oxide "button cell" batteries within the Light Tool, each of which produces approximately 1.2V.	 

The device manufacturer is:
IMPLICITCARE, LLC
[name]
[name]

5.0 MONITORING PROCEDURES

The Sponsor Standard Operating Procedure (SOP) for monitoring the investigative site will be followed. The sponsor will train the site following sponsor SOP's and may be present at initiation of treatment. The sponsor will also monitor the site periodically. The Investigator/Institution will permit trial-related monitoring, audits, IRB/IEC review, and regulatory inspections by providing direct access to source documents. The sponsor may request intermediate data following each visit to evaluate treatment progress. Case Report Forms will be reviewed for current data and Regulatory Binders will also be reviewed for correct documents. The sponsor will collect data at the end of the follow up period. The sponsor will list the study on clinicaltrials.gov when required by FDA regulations.

The monitoring plan for this study is outlined in the Cynosure Monitoring Plan.

ASSIGNED CLINICAL RESEARCH MONITOR:

Monitor #1
Name: [name]
Institution: Cynosure, LLC
Address: [name]

6.0 LABELING

Sample labeling will follow FDA regulations and the sponsor standard operating procedure. If applicable, the MyEllevate® device label will include, (in accordance with 801.1):

Statement: "CAUTION--Investigational device. Limited by Federal (or United States) law to investigational use."

Additionally, the label or other labeling will describe all relevant contraindications, hazards, adverse effects, interfering substances or devices, warnings, and precautions.

Directions for use are contained in the MyEllevate® IFU.

9.0 OTHER INSTITUTIONS

If a part of the study is conducted by an institution that has not previously been identified within the Investigational plan each institution's contact information will be documented below;

No other institutions will be part of this study.

10.0 ADDITIONAL RECORDS AND REPORTS

If this is an IDE study, additional records and reports will be maintained on the investigation in addition to those prescribed in 21 CFR 812 sub-part G. If this is a non-IDE study, the study summary will be maintained on the investigation and may include those prescribed in 21 CFR 812 sub-part G.

Additional Records and Reports:

Report	Submit To	Description/Constraints
N/A	N/A	This is a non-IDE study; no additional records or reports will be maintained.

11.0 PREGNANCY

Females may not participate in this study if they are pregnant, breastfeeding, were pregnant within the last three months or are planning a pregnancy during the study.

If the subject thinks they have become pregnant during the study, it is important that they inform the Investigator immediately. If she becomes pregnant or thinks that she may be pregnant, she will be removed from the study and will be asked to perform a final evaluation similar to the final follow-up visit. The Investigator may request to track the pregnancy and will report the pregnancy to the Sponsor.

12.0 SUBJECT WITHDRAWAL

The subject is free to withdraw from this study at any time. The subject must inform the Investigator immediately if they intend to withdraw. To terminate the subject's participation in this study, they must contact the Investigator at the contact information listed on page one of the informed consent form. They will be asked to come to the study clinic or Investigators office to complete a final follow up visit and may be asked to perform end of study procedures. Their decision to participate in this study or to withdraw from this study will not influence the availability of their future medical care and will involve no penalty or loss of benefits to which they are otherwise entitled.

The Investigator in charge of the study can remove the subject from this study without their consent for any reason, including, but not limited to:

- a) His/her judgment that any condition or circumstance may jeopardize their welfare or the integrity of the study.
- b) Their failure to follow the instructions of the Investigator(s).
- c) If the study is stopped by the sponsor and/or Investigators participating in the study prior to completion.

Data collected prior to withdrawal will be used in data analysis but after withdrawal no further data will be collected.

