1.2 Objectives

1. Primary Objective:
 - Safety assessment through the collection of Adverse Events.
2. Optional Assessments:
 - Collection of digital 2-D and/or 3-D photography.
 - Photographic evaluation with correct identification of pre-treatment images when compared to the 30 and 90 day follow-up images performed by blinded reviewers.
 - Principle Investigator assessment using the Global Aesthetic Improvement Scale (PGAIS) at the 30 and 90 day follow up visit.
 - Subject assessment using the Global Aesthetic Improvement Scale (SGAIS) at the 30 and 90 day follow up visit.
 - Subject satisfaction rates at the 30 and 90 day follow-up visit.
3. Additional Safety Objectives:
 - Collection of Discomfort/Pain Scores

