2.14 Adverse Event Recording

All data captured must be supported by the Investigator's timely assessment and documentation of the adverse event in the case report forms or source documents. All documented adverse events will be reviewed by the Sponsor or designee to determine whether the adverse event meets regulatory reporting requirements and to ensure timely adverse event reporting to meet local and global regulatory requirements. All adverse events must be followed until their resolution.

Adverse Events Pertaining to the MyEllevate® Procedure:

Mild discomfort during treatment may be experienced by the subject. Anticipated side effects include pain, edema (swelling) and erythema (redness), bleeding, bruising, and limitations in opening mouth.

Other possible side effects may include; dimpling, infection, poor wound healing, facial asymmetry, hematoma (fluid accumulation), numbness or other changes in skin sensation, temporary or permanent hair loss along incisions, scarring, burns (up to 3rd degree), tissue hardness, weakness of the lower lip, skin irregularities, skin discoloration, suture surfacing, deep venous thrombosis with cardiac or pulmonary sequelae, facial nerve paresis of the mandibular bands.

Adverse Events Pertaining to Anesthetic:

Pain and numbness may be experienced at the site of the injection. Other side effects may include redness, blanching, swelling, application site reaction, rash, infection, skin damage or nerve damage at the site of the injection. Temporary loss of sensation and muscle function at the site of injection, although uncommon, may also be experienced.

1% lidocaine (Lidocaine) with Epinephrine Injection

Lidocaine with epinephrine contains the preservative sodium metabisulfite which may cause allergic-type reactions including anaphylactic symptoms such as itching, hives, swollen areas of the body, and/or trouble breathing and life-threatening or less severe asthmatic episodes in certain susceptible people. If the subject has a reaction, medical attention may be provided or they may need to seek emergency care.

Adverse Events Pertaining to the Surgical Marker:

Using surgical marker has minimal risks and may produce effects on the body such as redness or a rash. Markings may remain visible for a few days or may be removed with alcohol.

Other Cautions:

Incomplete response or no response may occur since some subjects may not respond to treatment.

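### Section 12.0 ends data collection at withdrawal, even for treated subjects the Investigator removes; this conflicts with the adverse-event follow-up rules in 2.14 and 14.0 and could bias late-event percentages downward

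*Combined protocol and SAP*

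**What the plan says.** The primary objective in section 1.2 is "Safety assessment through the collection of Adverse Events". The treatment is a single procedure with a device kit whose suture is described in section 4.0 as "braided nonabsorbable polyester Suture". Section 2.14 lists suture surfacing among the possible side effects.

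On leaving the study, section 12.0 says three things:

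- A subject who intends to withdraw tells the Investigator. "They will be asked to come to the study clinic or Investigators office to complete a final follow up visit".
- The Investigator may remove a subject without consent. One listed ground is "His/her judgment that any condition or circumstance may jeopardize their welfare or the integrity of the study"; the others are not following instructions and a stop of the study.
- The section closes: "Data collected prior to withdrawal will be used in data analysis but after withdrawal no further data will be collected".

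On adverse events, section 2.14 says: "All adverse events must be followed until their resolution". Section 14.0 twice gives a somewhat wider list of end points: the event has resolved or settled, it has another explanation, or contact with the subject is lost. The second statement covers serious and non-serious events alike.

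On pregnancy, section 11.0 says that "she will be removed from the study and will be asked to perform a final evaluation similar to the final follow-up visit", and it allows the Investigator to ask to track the pregnancy.

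On analysis, section 2.15.3 bases the safety analysis on treated subjects with at least some safety data. Section 2.15.6 plans the number and percent of patients for each outcome, with no statistical comparisons.

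**The concern.** That the suture stays in the tissue is an inference, but a fair one from the device description and the suture-surfacing risk. On that reading, leaving the study ends observation but not exposure. A rule that stops collection at withdrawal then cuts into the primary objective in two ways. An event open at withdrawal may have no recorded resolution, and a new event after withdrawal is not recorded at all. The subject still counts in the denominator.

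Consent explains such a rule when a subject refuses further contact. It does not explain it for a subject removed by the Investigator, or for one who stops attending but would still answer questions. Removal on welfare grounds is plausibly linked to a complication, so the lost follow-up need not be a random part of the whole.

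**Working it through.** **Textual check.** The point rests on setting the rules side by side.

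1. Does the last sentence of 12.0 cover removal by the Investigator as well as voluntary withdrawal? It follows directly after the list of removal grounds, under the heading on withdrawal. Section 2.11 also speaks of subjects who have been withdrawn as well as those who withdraw. Read as written, it covers both.
2. Event open at withdrawal: 12.0 says collect nothing more; 2.14 says follow to resolution; 14.0 says follow to one of its listed end points, and withdrawal is not listed. This is a direct conflict.
3. New event after withdrawal: 14.0 records events from the first treatment onward and throughout the study, but does not say whether a withdrawn subject is still under observation. Section 12.0 settles it by excluding the event.
4. Final visit in 12.0 and final evaluation in 11.0: neither section says whether these fall before or after the point of withdrawal, so the status of their data is unclear. Pregnancy tracking under 11.0 would come after removal, and its status under 12.0 is also unclear.
5. Analysis: the subject remains in the safety set (2.15.3) and so in the denominator of the percentages (2.15.6), while later events cannot reach the numerator. Any resulting error in a late-event percentage is downward.

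**Scale.** The plan gives no figure to reproduce. Section 2.15.2 states 10 subjects, departures included, with no withdrawal rate, event rate or formula. From the documents: 10 subjects and 90 days of follow-up. The times and rates below are assumptions.

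- Share of the safety set per subject: 1/10 = 10%.
- Follow-up lost if removed at Day 7: (90 − 7)/90 = 83/90 = 92%. At Day 30: (90 − 30)/90 = 60/90 = 67%. These count calendar days, not events.
- If 2 of 10 leave early and both have a late event that is not collected, the report shows 0/10 instead of 2/10.
- With no event of a given type, the one-sided 95% upper bound is 1 − 0.05^(1/n). For n = 10 fully followed it is 25.9%; for n = 8 it is 31.2%. A report of 0/10 when only 8 were fully followed suggests more information than there is.
- Share of late events missed, if a fraction w leaves early and leavers have r times the risk of those who stay: w·r / [(1 − w) + w·r].

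| w | r = 1 | r = 3 |
|---|---|---|
| 0.1 | 0.1/1.0 = 10% | 0.3/1.2 = 25% |
| 0.2 | 0.2/1.0 = 20% | 0.6/1.4 = 43% |
| 0.3 | 0.3/1.0 = 30% | 0.9/1.6 = 56% |

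The r = 1 column shows that a simple percentage is too low even when withdrawal is unrelated to risk, because the denominator is not reduced for the missing follow-up.

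**The case against.** The strongest reply is that this is a small, uncontrolled study with descriptive safety summaries, that 2.14 and 14.0 already contain explicit follow-up duties, and that nothing is lost unless someone withdraws. Stopping collection is also proper when a subject withdraws consent to it. All of that stands. It lowers the severity, but it does not tell a site which rule to follow.

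Several stronger readings are tempting, and the documents do not support them:

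- A reader might infer that withdrawn subjects drop out of the safety assessment. They do not: 12.0 uses their earlier data and 2.15.3 keeps them in the safety set. Only later information is at risk.
- A reader might infer that the event leading to withdrawal goes unrecorded. It occurs before withdrawal, so it is counted. The requested final visit can capture its status, and 14.0 has outcome categories for unresolved events.
- A reader might infer that 2.15.3 contradicts 12.0, because "Everyone who begins the treatment is part of the study whether he or she completes the study or not". That sentence decides who is analysed and puts no collection duty on a site.
- A reader might take the final visits in 11.0 and 12.0 as plain contradictions. Both can be read as exit visits made before collection ends. The fault is that the text does not say.
- A reader might infer that those who leave are the subjects most likely to have complications. No data in the documents show this. Two removal grounds, study integrity and a study stop, need not involve a complication, and nothing links failure to follow instructions to higher risk.

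Replacement under 2.11 may restore the number of subjects, but not the follow-up of the one who left.

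**Conclusion.** The concern holds as a conflict between the last sentence of 12.0 and the adverse-event follow-up rules in 2.14 and 14.0, with an unclear status for the final visits and for pregnancy tracking. If sites follow 12.0 as written, late-event percentages for the primary objective could be biased downward. The direction follows from the safety set and the planned summaries. The size cannot be stated, because it depends on a withdrawal rate and on risks that the documents do not give; every figure above beyond 10 subjects and 90 days is an illustration. The point should be fixed, but it does not undermine the study.

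**What to change.** Reconcile 2.14, 11.0, 12.0 and 14.0 by replacing the last sentence of 12.0 with a rule that separates two things:

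- **Stopping participation.** For treated subjects who stop visits or are removed, and who do not refuse further contact, adverse-event collection continues through Day 90 and open events are followed as 14.0 already states. The form of contact should leave room for the tests and examinations that 14.0 calls for where appropriate.
- **Withdrawing consent to data collection.** Collection stops when the subject withdraws that consent; data already collected are kept.

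State that data from the final visit in 12.0 and the final evaluation in 11.0 are recorded and analysed, and state the status of pregnancy-tracking data. In the study report, give the number followed to Day 90 beside the adverse-event counts. The consent form was not among the material read, so its wording should be checked against the new rule.

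The cost is a one-paragraph amendment with IRB approval and, with up to 10 subjects, a few extra contacts. Sample size and treatment do not change. The small downside is some less complete safety data from subjects who no longer attend.
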